4.7 Screen failure procedures

All consented participants will receive a study ID number. Those who fail initial screening will be excluded and no information will be collected. If a participant failed initial screening due to temporary exclusion criteria (e.g., failed due to recent exacerbation, recent change in meds), the participant will be offered a re-screening visit for a future date outside of the exclusion window. Last name and partial MRN for participant failing screening will be retained during study recruitment on a secured document to prevent re-screening.

5 STUDY EVALUATIONS AND MEASUREMENTS

5.1 Data collection

5.1.1 Data abstracted from electronic medical charts

- Historical spirometry
- Evidence of any COPD exacerbation requiring systemic corticosteroids within the last three years
- Concurrent diseases
- Prescribed COPD medications
- Demographics: age, height, weight, gender

5.1.2. Questionnaires

The questionnaires administered will be the modified Borg dyspnea scale, modified Medical research Council, and the COPD Assessment Test. Additional questionnaires will capture exacerbations, medication adherence, and inhaler regimens. The questionnaires will be self-administered by study subjects or conducted by study personnel with the subjects when appropriate. For the mMRC (APPENDIX 2), mBorg (APPENDIX 3), and CAT (APPENDIX 4), the time period for subjects to self-assess symptoms is not specified. The modified Borg dyspnea scale will be used for home monitoring of respiratory status, whereas modified Medical Research Council

score, modified Borg scale, and CAT will be used for clinic visits (2, 6) as well the 4 telephone visits (3, 4, 5). In addition, CAT will be determined at the enrollment visit (Visit 1).

When questionnaires are administered by study personnel, they will be completed using a polite, professional, and non-judgmental tone. Pacing of the interview will be adjusted to each participant. Interviewers will be familiar with the forms and questionnaires they are administering. Familiarity allows the coordinator to maintain eye contact with the participant, which helps build rapport. The interviewer must be careful not to inadvertently change the wording of questions or instructions because he or she has partially memorized the interview. If a participant appears to not understand the question or provides an incomplete answer, the interviewer may employ several techniques to improve participant response. In the case of misunderstood questions, the interviewer may re-read the question with a different emphasis, stressing the part of the question the subject appears to have misunderstood. The interviewer should not modify the question wording. For incomplete answers, interviewers may use probing to further clarify a participant's answer. The most commonly used probing technique is silence. In this situation the interviewer waits for the participant to provide an answer. Participants may require time to recall events or consider how to respond. If the participant seems uneasy with the length of time he or she is taking to answer a question, the coordinator may reassure the participant, i.e., "Take your time" or "There is no rush."

5.1.3. Spirometry:

Historical spirometry will be abstracted from medical charts. If multiple spirometry records are available, the most contemporaneous will be abstracted. This will also include the age, height and weight at the time of spirometry.

5.1.4. PIFR Measurements

Study visits PIFR: PIFR measurements will be collected using the In-Check G16 DIAL® which is a simple, hand-held low range inspiratory flow device that measures PIFR via a brief inspiratory maneuver (APPENDIX 5). The device includes a one-way disposable mouthpiece, measurement diaphragm, and a directly visualized PIFR scale. The device also includes an adaptor with adjustable resistance to mimic nine resistance groups encompassing the popular MDIs and DPIs currently available. After each inspiratory maneuver to a set resistance, the PIFR score will be visualized on the scale and recorded. Subjects will perform the PIFR in the following manner:

Patients receiving Handihaler® and/or Ellipta® and/or Diskus® and/or Inhub®

- For testing during study visits, perform PIFR in the physical position they most commonly use when self-administering their maintenance inhaler(s)
- Perform PIFR using the inspiratory effort described by the manufacturer (Ellipta®, Diskus®, and Inhub®)- breathe out fully, then take a long, steady deep breath; ‘breathe out all the way, then breathe in slowly and deeply’ For the Handihaler®, subjects will be instructed as follows – “Empty your lungs of air. Breathe in deeply until your lungs are full.”
- Measurements will be collected on each prescribed DPI resistance setting. PIFR will be recorded with best approximation to nearest 1 L/min. Ample time will be given to any patients who may be feeling short of breath or fatigued.

Home measurement of PIFR: Using the In-Check G16 DIAL®

- Perform PIFR in physical position most commonly used when self-administering maintenance inhaler(s)
- Perform PIFR (proper setting) for each maintenance DPI patient is receiving
- Use maximum inspiratory effort, by first breathing out fully, and breathing in as hard and fast as possible, and as above, repeat the maneuver two more times, recording the highest value.

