Depending on the DPI, the minimum peak inspiratory flow rate (PIFR) ranges from 30 L/min for the Handihaler® to 60 L/min for the Diskus® and Ellipta® DPI's. ([name] 2017, Mahler 2017). The Handihaler® is a high-resistance DPI, whereas the Ellipta® and Diskus® are classified as medium-resistance inhalers. In vitro studies indicate that the fine particle dose from Diskus®, and Ellipta® DPIs can be reduced when inspiratory flow rate decreases below 60 L/min (Buttini, Feddah, Yokohama, Grant, Prime), whereas other studies showed little effect. (Hamilton) Recent studies in humans are finding that inhaled drug delivery with the Diskus® is suboptimal when the PIFR decreases below 60 L/min. In a study of healthy volunteers using the Diskus® inhaler, a decrease in the PIFR from 60 to 30 L/min resulted in 30% decrease in blood levels of albuterol and fluticasone ([Sulaiman 2017b](#)), indicative of decreased lung delivery. (Lipworth) A recent study evaluated errors made by COPD patients using the Diskus® over a one month period in the ambulatory setting post-hospitalization. For this study, an audio monitoring device (INCA) was attached to the inhaler to measure the inspiratory flow rate and monitor adherence. Subjects were educated on the proper use of the inhaler prior to discharge from the hospital. The most frequent error made by patients was an inadequate inspiratory effort in nearly one-half of the COPD patients. ([Sulaiman 2017b](#)) It is possible that PIFR may have been lower as a consequence of the recent exacerbation. In a study conducted in an outpatient research setting, using an instrumented Ellipta® inhaler, it was found that severe to very severe COPD patients had shorter inspiratory times and tended to have impaired inspiratory flow (< 60 L/min) through the device. (Prime) It appears that lung

delivery with the Diskus® and Ellipta® may be suboptimal between 30 L/min and 60 L/min. The aforementioned data is the basis for the use of target PIFR values for Handihaler®, Diskus®, and Ellipta® devices (30 L/min, 60L/min, and 60 L/min, respectively) for the current study. We have also chosen to only enroll patients with a PIFR \leq 90 L/min at a medium resistance PIFR setting (Ellipta®) in order to select a cohort that has a reasonable probability that their PIFR may approach the minimally acceptable value for their prescribed DPI(s) with worsened symptoms.

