3.4 Study Population

Our study population will be outpatients with moderate, severe, or very severe COPD.

Participants will be recruited from multiple sources as described above.

Inclusion Criteria:

- Age > 50 years-old
- Spirometry-confirmed diagnosis of COPD (FEV1/FVC <0.70)
- GOLD II-IV based on existing spirometry results
- CAT score > 10
- For high resistance DPI, baseline PIFR < 90 L/min (InCheck DIAL®) and >=30 L/min; for medium resistance DPI, PIFR ≤ 90 L/min (InCheck DIAL®) and >=60 L/min. Handihaler is a high resistance DPI. Examples of medium resistance DPI: Anoro, Incruse, Breo Ellipta®, Advair® Diskus®, or Wixela® Inhub® DPI
- History of smoking tobacco products > 10 pack years
- Prescribed at least one daily maintenance DPI with no change in prescription within the four weeks prior to the Enrollment Visit
- One or more exacerbations of COPD requiring systemic corticosteroids within last 3 years
- Patients will be enrolled with regards to the below pre-specified characteristics based on gender and the prescribed maintenance inhaler(s) as follows (note that patients are commonly prescribed multiple inhalers):
 - Male : Female ratio 1:1 (+ 10%)
 - Target recruitment stratified to two treatment arms:

- N=60 patients receiving medium resistance DPI (Anoro, Incruse, Breo Ellipta®, Advair® Diskus®, or Wixela® Inhub® DPI) with planned recruitment to include 50% of participants on Diskus® and 50% on Ellipta®
- N= 60 patients receiving high resistance DPI (Spiriva Handihaler® DPI)

For all study participants, participants may also receive another MDI, Respimat® inhaler, or DPI (e.g. Breo Ellipta® + Spiriva Respimat®, Symbicort MDI® + Spiriva Handihaler®, Advair Diskus® + Spiriva Handihaler®, Wixela® Inhub® + Spiriva Handihaler®) Subjects will be placed into one of the two cohorts based on the DPI, if on more than one DPI, they will be placed into the cohort for the DPI with the highest resistance (Handihaler>Ellipta=Diskus=Inhub). These strata are for recruitment only, and PIFR measurement for both DPIs will be recorded and used in analyses.

Exclusion Criteria:

- Inability to demonstrate proper technique for the InCheck DIAL® device
- Inability to achieve minimum PIFR for prescribed DPI(s) at screening/enrollment visit (< 30 L/min for e.g., Handihaler® (High resistance DPI), < 60 L/min for Ellipta® (Medium resistance DPI))
- Neuromuscular disease associated with weakness

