4.2 Study Visits

There will be six study visits/encounters over a 22-26 week period as shown in the Study Procedures and Assessments Table. Two study visits will occur at the UNC Clinics (Visits 1 and 2)

and four visits will only involve a telephone interview of subjects by study personnel (Visits 3, 4, 5, and 6).

Visit 1- Screening Visit

At Visit 1, after obtaining written informed consent, a clinical history will be obtained from the patient and if the subject meets all inclusion and exclusion criteria, a CAT score will be determined. The patient will undergo PIFR assessment based on prescribed DPI. PIFR will be recorded with best approximation to nearest 1 L/min. Subjects will be excluded if PIFR > 90 L/min based on Ellipta® and Diskus® setting or inability to achieve minimum PIFR for prescribed DPI setting (< 30 L/min for Handihaler®, < 60 L/min for Ellipta®, Diskus®, or Inhub®). The PIFR will be performed in triplicate by the patient at the recommended device setting (based on patient's DPI specific internal resistance) in the physical position (e.g. sitting) that the patient normally uses to self-administer their inhaler(s). Further, they will be instructed to perform the PIFR consistent based on the manufacturer instructions for proper DPI inhalation technique (e.g. Ellipta®, Diskus® DPI, , Inhub®) "Breathe out gently and breathe in steadily and deep"). For the Handihaler®, subjects will be instructed as follows – "Breathe out completely in one breath. Empty your lungs of air. Breathe in deeply until your lungs are full." If the patient meets the inclusion and exclusion criteria including a PIFR < 90 L/min, they can proceed to Visit 2 (Enrollment) either during the same encounter or scheduled within 30 days. If there is greater than 30 days between Visit 1 and 2, another informed consent will be reviewed and signed.

For inclusion, historical spirometry is required to be documented to ensure patients meet the GOLD definition of COPD using airflow obstruction. Most recent spirometry data will be used for characterization of the enrolled cohort. No spirometry testing will be performed as part of this study.

Visit 2- Enrollment Visit

- A physical examination including measurement of waist circumference (measured in inches horizontally through the narrowest part of the torso, between the lowest rib and the iliac crest)
- Medical history (includes exacerbations history)
- COPD medication use (maintenance and reliever)

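### For Ellipta, Diskus and Inhub, eligibility is read on a steady or slow clinic breath and sPIFR on a maximal home breath, and the plan does not reconcile the two

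*Combined protocol and SAP*

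**What the plan says.** **Clinic, medium resistance.** Section 4.2 (Visit 1) tells Ellipta, Diskus and Inhub users: "Breathe out gently and breathe in steadily and deep". Section 5.1.4, for study visits, gives two further wordings for the same devices: "breathe out fully, then take a long, steady deep breath" and "breathe out all the way, then breathe in slowly and deeply". The two sections also disagree on whether the patient first breathes out gently or fully.

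**Clinic, Handihaler.** Section 5.1.4 says "Breathe in deeply until your lungs are full", with nothing on speed or force.

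**Home, every device.** Section 5.1.4 says "Use maximum inspiratory effort, by first breathing out fully, and breathing in as hard and fast as possible". Section 4.1 adds that the best of three efforts is recorded, but describes no technique.

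**Where the clinic reading is used.** Section 4.2 states "Subjects will be excluded if PIFR > 90 L/min based on" the medium-resistance settings, and also excludes readings under 30 (Handihaler) or 60 L/min (the others). Section 3.4 words the floor as "Inability to achieve minimum PIFR for prescribed DPI(s) at screening/enrollment visit". Section 1.3 explains the ceiling as a way to "select a cohort that has a reasonable probability that their PIFR may approach the minimally acceptable value" for the prescribed inhaler.

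**Where the home reading is used.** Section 6.1 defines sPIFR as two readings in a row, on separate days, under the same 30 or 60 L/min cut-off. It names neither manoeuvre nor setting. The full analysis set in section 6.3 likewise asks for two consecutive readings without saying where they were taken. Visits 3 to 6 are telephone calls, so every PIFR reading after Visit 2 is a home reading.

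**The concern.** Peak inspiratory flow depends on effort. A patient told to breathe in slowly and a patient told to breathe in as hard as possible are not giving the same measurement. The plan nevertheless applies the same floors of 30 and 60 L/min to both, first to decide entry and then to count the primary event. The reason section 1.3 gives for the 90 L/min ceiling, that admitted patients may drift down towards the minimum, holds only if entry and follow-up readings lie on one scale.

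What is at stake depends on what sPIFR is meant to measure:

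- **Maximal ability.** The home reading is the right one and the clinic screen is the mismatched half. Some medium-resistance patients may be turned away, or let in, who would not be under the endpoint's own manoeuvre.
- **Usual technique.** The clinic reading is the right one, and home readings may sit too high, so that sPIFR is under-counted.

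A second, smaller gap is that sections 6.1 and 6.3 do not stop a clinic reading from forming half of a consecutive pair.

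**Working it through.** **Step 1: the manoeuvres side by side.**

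| Setting | Devices | Breathing out | Breathing in | Use |
|---|---|---|---|---|
| Clinic, 4.2 | Ellipta, Diskus, Inhub | gently | steady, deep | floor 60, ceiling 90 |
| Clinic, 5.1.4 | Ellipta, Diskus, Inhub | fully | steady or slow, deep | same |
| Clinic, 4.2 and 5.1.4 | Handihaler | completely | deep, speed not given | floor 30 |
| Home, 5.1.4 | all | fully | maximal, hard and fast | sPIFR at 30 or 60 |

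No section links these rows. Section 1.3 adds two more descriptions: a dry powder inhaler needs a fast, deep inhalation, and the In-Check measurement is a short inhalation of 1 to 2 seconds. The direct contradiction concerns the medium-resistance devices; for the Handihaler the clinic text is only incomplete.

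**Step 2: which target the documents favour.** The synopsis rationale speaks of patients' ability to generate enough effort. Section 1.3 describes the device as testing ability to reach a minimum effort. Section 3.4 excludes for inability. Section 4.1 records the highest of three efforts, and section 5.1.4 asks for maximum effort at home. All point to maximal ability, but section 6.1 does not say so.

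**Step 3: what a clinic reading could do in a pair.** Visit 2 takes readings in three positions, including lying at 45°, and before and after a bronchodilator. An eligible patient should be at or above the floor in the usual position, but nothing prevents a lower reading in another position from pairing with the first home reading. Visits 1 and 2 on different days could also meet the full-analysis-set rule with no home reading at all.

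**Step 4: possible size on the maximal-ability reading (illustration only).** Inputs: the pilot Diskus mean of 61 and SD of 13 L/min (section 1.3), taken as normal and as clinic-script values. The documents do not say which manoeuvre the pilot used. Measurement noise is ignored. Assumption: maximal effort multiplies the reading by (1 + k), with k from 0 to 20%. Φ is the standard normal distribution function.

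- Below the floor on the clinic reading: Φ((60 − 61)/13) = 0.4693.
- Admitted (60 to 90): Φ((90 − 61)/13) − 0.4693 = 0.9872 − 0.4693 = 0.5179.
- Share of those below 60 who would reach 60 maximally: [0.4693 − Φ((60/(1+k) − 61)/13)] / 0.4693.
- Share of those admitted who would exceed 90 maximally: [0.9872 − Φ((90/(1+k) − 61)/13)] / 0.5179.

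| k | Screened out but could reach 60 | Admitted but would exceed 90 |
|---|---|---|
| 0 | 0% | 0% |
| 5% | (0.4693 − 0.3834)/0.4693 = 18% | (0.9872 − 0.9714)/0.5179 = 3% |
| 10% | (0.4693 − 0.3098)/0.4693 = 34% | (0.9872 − 0.9454)/0.5179 = 8% |
| 20% | (0.4693 − 0.1987)/0.4693 = 58% | (0.9872 − 0.8592)/0.5179 = 25% |

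**Step 5: the planned precision.** The plan's N = 120 reproduces: 1.96² × 0.4 × 0.6 / 0.088² = 119.05, rounded up to 120. The mismatch does not change that arithmetic.

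**The case against.** The strongest reply is that the endpoint itself is sound. If maximal ability is the target, every home reading follows one script against fixed cut-offs, and the proportion correctly describes the patients enrolled. That stands: on this reading the issue is who was enrolled, not a bias in counting their events.

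A reader might go further and infer that the primary proportion is under-counted by more than the planned half-width of 8.8 points. The documents do not support that. It requires the less favoured target (usual technique), and it requires a technique effect and a within-patient SD that the plan does not give. In a simulation with 72 independent home sessions, screening on two readings, one inhaler per patient and only medium-resistance values shifted, an assumed SD of 5 L/min gives pooled sPIFR of about 26%, 19%, 15% and 12% at shifts of 0, 5, 10 and 20%. The 10% shift (11 points) exceeds 8.8 and the 5% shift (7 points) does not. At SD 3 in the same model no shift up to 20% exceeds it. The level is mostly a product of the assumptions.

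A reader might also infer that the PIFR and CAT association mixes manoeuvres. Section 6.3 lists Visit 1 alongside Visits 3 to 6 but does not say that they are pooled; analysed visit by visit, nothing is mixed.

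It can also be argued that the clinic wording paraphrases manufacturers' instructions and that section 1.3's fast or brief inhalation is what would happen in practice. That may narrow the true difference, but it leaves one more description to reconcile. Taking the best of three does not help either: the best of three slow breaths is still a slow breath.

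Finally, technique arguably belongs in section 5.1.4 and not in 6.1. That is fair as a matter of layout, but 5.1.4 contains both manoeuvres and 6.1 does not restrict sPIFR to home readings.

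**Conclusion.** The point holds as a contradiction in the measurement instructions and should be fixed. For medium-resistance inhalers, following the plan means applying the same cut-offs to two different manoeuvres, one for entry and one for the primary endpoint. Confidence in the textual mismatch is high. The size of its effect is unknown and may be nil, because the documents give no technique effect.

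On the better-supported target the consequence is for eligibility and generalisability: at an assumed 5% or 10% effect, 18% or 34% of those under the floor, and 3% or 8% of those admitted, would be classed differently. These figures rest on the pilot mean and SD, normality, no measurement noise, and the assumption that a forceful breath gives a higher reading. On the less supported target sPIFR may be under-counted, by an amount that cannot be stated from the documents. The sample-size calculation is unaffected.

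**What to change.** 1. Reconcile sections 4.2 and 5.1.4 to one manoeuvre per device, chosen by the sponsor and used at Visits 1 and 2 and at home. State in section 6.1 that this manoeuvre defines sPIFR. If the home script is kept and the clinic script is aligned to it for new screenings, the endpoint series stays uniform across patients. If the home script is changed instead, patients already in follow-up keep theirs, and the sPIFR proportion is also reported by script version.
2. In section 6.1 and in the full-analysis-set definition in section 6.3, count only home readings towards the two consecutive measurements.
3. For patients already screened under the current clinic wording, report associations that use the clinic (Visit 1) PIFR separately from those that use home PIFR, and state the eligibility mismatch as a limitation.

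A table of home-minus-clinic differences by device is optional. If produced, it should note that the difference also carries setting effects and regression to the mean. A redefined baseline and counts of home readings outside the entry limits are not needed.

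The cost is wording in sections 4.2, 5.1.4, 6.1 and 6.3, and a revised notebook page for new patients only if the home script changes. There are no extra visits or measurements.

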5.1.4.1 Efficacy Evaluation (if applicable)

Changes in PIFR and dyspnea (modified Borg) that occur in the COPD population in the home setting during periods of stable respiratory symptoms and periods of worsening will be measured and recorded by participating subjects. PIFR measurements, PRO (mMRC, modified Borg, CAT) will also be undertaken in the research clinic setting. PRO will also be completed with each telephone-based study visit.

5.1.4.2 Safety Evaluations

Measurement of PIFR will be deferred or not performed for those with chest, abdominal, oral or facial pain; stress incontinence; dementia; recent myocardial infarction (6 weeks), chest or abdominal or ocular surgery (6 weeks), those with prior significant difficulties with spirometry or participant refusal.

6 STATISTICAL CONSIDERATION

6.1 Primary Endpoint

For each patient the occurrence of suboptimal Peak Inspiratory Flow Rate (sPIFR) over 24 weeks. sPIFR will be defined as any two consecutive measurements on different days below the optimal threshold for any prescribed DPI (e.g., <30 L/min for Handihaler® (High resistance DPI), <60 L/min for Ellipta® (Medium resistance DPI))

